8.4.2.1.3. Evaluation of Clinical Laboratory Values

The normal ranges of values for the clinical laboratory assessments in this study will be provided by the responsible laboratory and submitted to TLC before the beginning of the study. They will be regarded as the reference ranges on which decisions will be made.

If a laboratory value is out of the reference range, it is not necessarily clinically significant. The investigator must evaluate the out-of-range values.

All clinical laboratory values that in the investigator's opinion show clinically significant or pathological changes during or after termination of treatment must be reported as AEs and followed, as described in Section 9.2.

All measurements described in this section are recognized standard methods.

8.4.2.2. Clinical Examinations

8.4.2.2.1. Vital Signs

Vital signs (heart rate, respiratory rate, sitting blood pressure, and temperature) will be measured after the patient has been in a sitting position for 5 minutes.

Height and weight will be measured at Screening only.

8.4.2.2.2. Twelve-lead Electrocardiogram

A standard 12-lead ECG will be performed after the patient has been supine for at least 5 minutes. All ECG recordings will be identified with the patient number, date, and time of the recording and recorded in the patient's eCRF.

8.4.2.2.3. Physical Examination

The following physical examination will be performed at the time points indicated in the schedule of events (Section 1.1):

- General Appearance
- Head/Face
- Eyes/Fundoscopy
- Ears/Hearing
- Nose
- Mouth, Teeth, and Throat
- Neck and Thyroid
- Chest/Lungs
- Abdomen
- Skin, Hair, and Nails
- Musculoskeletal: Extremities, Spine
- Vascular/Circulatory
- Lymphatic
- Psychiatric/Behavior
- Brief neurologic

8.4.2.2.4. Knee Radiographs

A posterior-anterior X-ray radiograph will be performed for both knees (as applicable) in standing fixed-flexion (approximately 20 degrees) at the time points indicated in the schedule of events (Section 1.1). Minimum joint space width (in unit of millimeter) in the standing fixed-flexion anteroposterior view will be measured and recorded for analysis. Presence or absence of subchondral bone changes, osteonecrosis, and insufficiency fracture will be assessed.

9. ADVERSE EVENTS

9.1. Definitions

9.1.1. Adverse Events

An AE is defined as any untoward medical occurrence in a patient or clinical investigation patient administered a pharmaceutical product that does not necessarily have a causal relationship with this treatment. An AE can therefore be any unfavorable and unintended sign (including an abnormal laboratory finding, for example), symptom, or disease temporally associated with the use of a medicinal product, whether or not related to the medicinal product.

Pre-existing diseases or conditions will not be considered AEs unless there is an increase in the frequency or severity, or a change in the quality of the disease or condition. (Worsening of a pre-existing condition is considered an AE.)

9.1.2. Serious Adverse Events

An SAE is any untoward medical occurrence that at any dose:

- Results in death
- Is life-threatening

NOTE: The term “life-threatening” in the definition of “serious” refers to an event in which the patient was at risk of death at the time of the event; it does not refer to an event that hypothetically might have caused death if it were more severe.

- Requires inpatient hospitalization or prolongation of existing hospitalization

An elective hospital admission to treat a condition present before exposure to the study drug, or a hospital admission for a diagnostic evaluation of an AE, does not qualify the condition or event as an SAE.

- Results in persistent or significant disability/incapacity

- Is a congenital anomaly

NOTE: A congenital anomaly in an infant born to a mother who was exposed to the study drug during pregnancy is an SAE. However, a newly diagnosed pregnancy in a patient that has received a study drug is not considered an SAE unless it is suspected that the study drug(s) interacted with a contraceptive method and led to the pregnancy.

- Is an important medical event

NOTE: Medical and scientific judgment should be exercised in deciding whether it is appropriate to consider other situations serious, such as important medical events that may not be immediately life-threatening or result in death or hospitalization but may jeopardize the patient or may require intervention to prevent one of the other outcomes listed in the definition above. Examples of such events are intensive treatment in an emergency room or at home for allergic bronchospasm, blood dyscrasias, or convulsions that do not result in hospitalization, development of drug dependency, or drug abuse.

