8.1.1. Phone Visits

On the scheduled day of the phone visit, site staff shall contact the patient by phone and conduct all study procedures that do not require direct physical contact (e.g., laboratory tests, physical examinations, radiographs, etc.). Adverse event and concomitant medication review should occur as per usual procedure.

Patients with symptoms of potential adrenal insufficiency should be encouraged to visit the study site for a laboratory test. If the study site is closed for patient's visiting, the patient should be referred to a local laboratory, urgent care, primary care physician, or emergency room for testing and/or follow-up as appropriate.

Prior to the phone call, the site staff will activate visit date in the electronic data capture (EDC) system. Site staff should enable the Patient Diary Activation for the site visit in interactive response technology. Site staff will confirm with the patient that assessments have populated. If the daily diary is not functioning during the call, the site will need to manually document the patient's responses on paper assessments. Then contact their assigned CRA for instructions on how to enter responses into the EDC manually.

If the study site is closed, site staff will work from home calling patients and use the EDC website provided - <https://login.imedidata.com/login>. There is no change in username/password. The process for entering the date of visit is the same whether or not the user is working from the office. Site staff should remain in contact with the Principal Investigator and keep them aware of the patients' condition to ensure patient safety. The authorized investigator should be responsible for any medical judgment (when needed) and/or monitoring of potential symptom of adrenal insufficiency (local laboratory test for cortisol can be taken if it is medically urgent).

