9.2.2.2. Seriousness

The investigator is to evaluate whether the AE meets serious criteria.

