10. DATA SAFETY MONITORING BOARD

A data safety monitoring board will not be used in this study.

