11.3.4.1. Adverse Events

The Medical Dictionary for Regulatory Activities terminology will be used to classify all AEs with respect to system organ class (SOC) and PT.

Treatment-emergent AEs are defined as AEs with onset at the time of or following the start of treatment with study drug through EOS or ET, whichever occurs first.

The number and percentage of patients with AEs will be displayed for each treatment group by SOC and PT. Summaries of AEs by severity and relationship to study drug will also be provided. Serious AEs and AEs resulting in discontinuation of study drug will be summarized separately in a similar manner. Patient listings of AEs, SAEs and AEs causing discontinuation of study drug will be produced.

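### Section 9.1.2 exempts every diagnostic hospital admission from the seriousness criterion, so an adverse event admitted unplanned for work-up only can escape SAE reporting

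*Combined protocol and SAP*

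**What the plan says.** Section 9.1.2 lists the criteria that make an adverse event serious. One of them is "Requires inpatient hospitalization or prolongation of existing hospitalization". The sentence directly beneath it takes two kinds of admission out of that criterion. The first is "An elective hospital admission to treat a condition present before exposure to the study drug". The second is introduced by a fresh noun phrase: "a hospital admission for a diagnostic evaluation of an AE, does not qualify the condition or event as an SAE".

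The section keeps the criteria for death, threat to life, disability and congenital anomaly, and a further one for important medical events, where "Medical and scientific judgment should be exercised in deciding whether it is appropriate to consider other situations serious".

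Section 9.2.2.2 leaves the classification to the site: "The investigator is to evaluate whether the AE meets serious criteria". Section 9.2.5.1 requires SAEs, whatever their suspected cause, to be sent to the safety officer within 24 hours. Section 11.3.4.1 says that "Serious AEs and AEs resulting in discontinuation of study drug will be summarized separately", with listings to match. Section 10 states that "A data safety monitoring board will not be used in this study".

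**The concern.** The first exemption is sound. A planned admission for a condition the patient already had says nothing about the study drug. The second is of another kind, because its subject is an adverse event, which may be new and may follow an injection. An unplanned inpatient stay to find out what is wrong with such a patient is a central case of the hospitalization criterion, yet the text removes it.

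What is at stake is classification. Only events classed as SAEs go to the safety officer within 24 hours and enter the SAE tables. If the definition drops some of them, rapid sponsor review does not happen for those events and the SAE count in the study report is too low. The point carries more weight because no safety board will look across the arms during the trial. It does not touch the primary endpoint or any efficacy analysis.

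**Working it through.** The plan states no figure on this point, so the check sets the passages against each other.

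**Step 1: scope of the exemption.** In the first limb, two limits apply: the admission is elective, and the condition predates exposure. The second limb starts again with its own noun and carries neither limit. Nor does it limit length of stay or require that the work-up prove negative. It therefore covers emergency admission for a new event.

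**Step 2: apply Section 9.1.2 to the possible cases.**

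| Case | Hospitalization criterion | Exempting sentence | Class as written |
|---|---|---|---|
| Planned admission for a condition present before exposure | Met on its face | First limb applies | Not serious, reasonably |
| AE after dosing, admitted for treatment | Met | Does not apply | SAE |
| AE after dosing, admitted for work-up, also life-threatening or judged an important medical event | Met | Second limb applies | SAE by the other criterion |
| AE after dosing, unplanned inpatient admission for work-up only, no other criterion met | Met | Second limb applies | **Not an SAE** |
| Admission that begins as work-up and turns into treatment | Met | Unclear | **No rule; left to each site** |

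The fourth and fifth rows are the defect. An existing stay that is prolonged is not affected, because the exemption speaks only of admission.

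**Step 3: follow the fourth row downstream.** The investigator applies the criteria (Section 9.2.2.2) and records the event as non-serious. The 24-hour duty in Section 9.2.5.1 is triggered only by SAEs, so it does not apply. The separate summary and listing in Section 11.3.4.1 draw on the same classification, so the event is absent there too.

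**Step 4: what still catches the event.** Section 9.2.1 has all AEs documented. Section 9.2.3 has each one marked as to whether it is of special interest and whether it may be a sign of adrenal insufficiency. Section 11.3.4.1 tabulates all AEs by system organ class, preferred term, severity and relationship. The data are kept; the serious label and the rapid report are what is lost.

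**Step 5: size.** The number affected would be

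affected = N × a × w × u

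where N is the number treated (about 500 planned), a the proportion admitted for an AE, w the share of those admitted for work-up only, and u the share of those meeting no other criterion. The documents give N and none of a, w or u, so no count can be derived.

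**The case against.** The best case for the plan is that the sentence is an explicit exception, placed under the criterion it qualifies, much as the note on pregnancy qualifies the congenital-anomaly criterion. A reader might infer that the section flatly contradicts itself. It does not: it states a rule and then an exception, and the fault is that the exception is too wide. That part of the objection stands.

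A reader might also infer that admissions for adrenal insufficiency or joint infection are kept out of SAE reporting as a class. The documents do not support that. The clause names neither. A joint infection or adrenal event admitted for treatment remains an SAE, as does one that threatens life or is judged medically important. For adrenal risk there is also a dedicated route: Section 9.3.1.1 has an unblinded medical monitor review all cortisol values and has signs and symptoms assessed at every visit or contact. Section 8.1.1, on phone visits under COVID-19 restrictions, says that if the site is closed "the patient should be referred to a local laboratory, urgent care, primary care physician, or emergency room for testing and/or follow-up as appropriate". None of that is described as inpatient admission, so it does not show that the clause would be used for these patients. The text on events of special interest in Section 9.3.1 is incomplete in the public copy and cannot be used either way.

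The remaining criteria do not close the gap, however. The important-medical-event route is discretionary and is framed around situations that may not lead to hospitalization. An investigator who has just read that a diagnostic admission does not make an event serious has little prompt to use it. The special-interest and adrenal flags are not tied, in the visible text, to the 24-hour report. Cortisol review does not cover events unrelated to the adrenal axis.

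**Conclusion.** Wrong as written; it should be fixed. The conclusion rests on the wording alone: the diagnostic limb has no limits, and both the 24-hour report and the SAE tables depend on the classification it alters. It assumes only that sites follow Section 9.1.2 literally. The affected group is confined to events whose sole claim to seriousness is an inpatient admission for work-up, plus the unclassified admissions that pass from work-up to treatment.

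Two further inferences should be resisted. One is that the undercount would fall more heavily on TLC599 than on placebo. That would need admission rates by arm, which the documents do not give. The other is that expedited reports to authorities would be lost. The visible text sets out the report to the safety officer and otherwise refers investigators to applicable regulations, so the claim should stop at the 24-hour report.

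**What to change.** In Section 9.1.2, either delete the limb that exempts diagnostic admissions, or confine it to planned admissions where no AE itself required inpatient admission or met another seriousness criterion. Add that an admission that starts as work-up and becomes treatment counts as hospitalization. Keep the exemption for elective admission for a condition present before exposure.

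Before database lock, and blinded to treatment, re-review any admissions already classed as non-serious under the clause. This is feasible because Section 1 places lock after the last patient has completed the study.

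The cost is a protocol amendment of one clause and one added sentence, the re-review, a few more SAE reports and a slightly higher SAE count.

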9.1.3. Treatment-emergent Adverse Events

An AE is defined as treatment emergent if the first onset or worsening at the time of or following the start of treatment with study drug through the Follow-up Visit or ET, whichever occurs first.

9.2. Event Assessment and Follow-up of Adverse Events

Any AE will be followed to a satisfactory resolution, until it becomes stable, or until it can be explained by a known cause (i.e., concurrent condition or medication) and clinical judgment indicates that further evaluation is not warranted. All findings relevant to the final outcome of an AE must be reported in the patient's medical record and recorded on the eCRF page.

9.2.1. Collection

The investigator is responsible for the detection and documentation of events meeting the criteria and definition of an AE or SAE described previously. At each visit, the patient will be allowed time to spontaneously report any issues since the last visit or evaluation. The investigator will then monitor and/or ask about or evaluate AEs using non-leading questions, such as the following:

- “How are you feeling?”
- “Have you experienced any issues since your last visit?”
- “Have you taken any new medications since your last visit?”

Any clinically relevant observations (including laboratory abnormalities) made during the visit will also be considered AEs. All AEs observed by the study personnel or reported by the patient during the study (after the patient has signed the ICF through the EOS/ET visit) will be documented.

9.2.2. Evaluation

9.2.2.1. Severity of Adverse Events

The clinical severity of an AE will be classified as:

Mild	Usually transient and may require only minimal treatment or therapeutic intervention. The event does not generally interfere with usual activities of daily living.
Moderate	Usually alleviated with additional specific therapeutic intervention. The event interferes with usual activities of daily living, causing discomfort but poses no significant or permanent risk of harm to the patient.
Severe	Interrupts usual activities of daily living, or significantly affects clinical status, or may require intensive therapeutic intervention.

It is important to distinguish between severe AEs and SAEs. Severity is a classification of intensity whereas an SAE is an AE that meets serious criteria.

9.2.2.2. Seriousness

The investigator is to evaluate whether the AE meets serious criteria.

9.2.2.3. Action(s) Taken

Action taken may consist of the following:

Not applicable	Determination of a value is not relevant in the current context.
Unknown	Not known, not observed, not recorded, or refused.
Other action taken	Specify other action taken.

9.2.2.4. Outcome at the Time of Last Observation

The outcome at the time of last observation will be classified as:

- Recovered/resolved
- Recovered/resolved with sequelae
- Recovering/resolving
- Not recovered/not resolved
- Fatal*
- Unknown

*Only select fatal as an outcome when the AE results in death. If more than 1 AE is judged to be possibly related to the patient's death, the outcome of death should be indicated for each such AE. Although "fatal" is usually an event outcome, events such as sudden death or unexplained death should be reported as SAEs.

9.2.2.5. Adverse Event Relationship to Study Drug

The investigator must make an assessment of each AE's relationship to the study drug. The categories for classifying the investigator's opinion of the relationship are as follows:

Not related	An AE with sufficient evidence to accept that there is no causal relationship to study drug administration (e.g., no temporal relationship to drug administration, because the drug was administered after onset of event; investigation shows that the drug was not administered; another cause was proven.)
Unlikely related	An AE, including laboratory test abnormality, with a temporal relationship to study drug administration that makes a causal relationship improbable, and in which other drugs, events, or underlying disease provide plausible explanations.
Possibly related	An AE with a reasonable time sequence to administration of the study drug, but that could also be explained by concurrent disease or other drugs or events. Information on drug withdrawal may be lacking or unclear.

Probably related	An AE with evidence to suggest a causal relationship, and the influence of other factors is unlikely. The clinical event, including an abnormal laboratory test result, occurs within a reasonable time after administration of the study intervention, is unlikely to be attributed to concurrent disease or other drugs or chemicals, and follows a clinically reasonable response on withdrawal (de-challenge). Re-challenge information is not required to fulfill this definition.
Definitely related	An AE occurring in a plausible time relationship to study drug administration and that cannot be explained by a concurrent disease or other drugs or events. The response to withdrawal of the drug (de-challenge) is clinically reasonable.

9.2.3. Documentation

All AEs that occur within the period of AE follow-up for the study must be documented in the eCRF with the following information, where appropriate. (The AE follow-up period for the study is described in Section 9.2.)

- AE name or term
- When the AE first occurred (start date and time)
- When the AE stopped (stop date and time or an indication of “ongoing”)
- Severity of the AE
- Seriousness (hospitalization, death, etc.)
- Actions taken
- Outcome
- Investigator opinion regarding the AE relationship to the study drug(s)
- Whether it is an AE of special interest (AESI) and whether it is an AE which is a potential symptom or sign of adrenal insufficiency (AEAI) (see Section 9.3.1)

9.2.4. Treatment of Adverse Events

Adverse events that occur during the study will be treated, if necessary, by established standards of care. The decision about whether the patient may continue in the study will be made by the sponsor after consultation with the investigator and/or medical monitor.

If AEs occur in a patient that are not tolerable, the investigator must decide whether to stop the patient’s involvement in the study and/or treat the patient. Special procedures may be recommended for the specific study drug, such as the collection of a serum sample for determining blood concentrations of study drug, specific tapering procedures, or treatment regimens, as appropriate.

For double- or triple-blinded studies, it is not necessary to unblind a patient’s treatment assignment in most circumstances, even if an SAE has occurred. If unblinding is necessary, see Section 7.7 for a description of the unblinding procedures.

9.2.5. Reporting

9.2.5.1. Serious Adverse Events

Any SAE must be reported by the investigator if it occurs during the clinical study or within 30 days of receiving the study drug, whether or not the SAE is considered to be related to the investigational product. A copy of SAE forms and supporting documents must be emailed within 24 hours to the attention of the safety officer at:

At the time of first notification, the investigator or designee should provide the following information, if available:

- Protocol number
- Reporter (study site and investigator)
- Patient's study number
- Patient's year of birth
- Patient's gender
- Date of first dose of study drug(s)
- Date of last dose of study drug(s), if applicable
- Adverse event term
- Date of occurrence of the event
- A brief description of the event, outcome to date, and any actions taken
- The seriousness criteria(on) that were met
- Concomitant medication at onset of the event
- Relevant medical history information
- Relevant laboratory test findings
- Investigator's opinion of the relationship to study drug(s) ("Is there a reasonable possibility that the study drug caused the SAE? Yes or No?")
- Whether and when the investigator was unblinded as to the patient's treatment assignment

Any missing or additional relevant follow-up information concerning the SAE should be sent to the sponsor/sponsor representative via the same contact details above as soon as possible on a follow-up SAE Report Form, together with the following minimal information (initial report, AE, date of occurrence, patient identification, study identification, study drug, and site number); this will allow the follow-up information to be linked to the initial SAE report.

Specific information may be requested by [REDACTED] using a follow-up request form or via email communication.

The investigator is required to comply with applicable regulations (including local laws and guidance) regarding the notification of his or her health authorities, institutional review board (IRB)/independent ethics committee (IEC), principal and coordinating investigators, study investigators, and institutions. Each investigator is obligated to learn about the reporting requirements for investigators in his or her country. The study monitor may be able to assist with this.

